Buprenorphine Induction and Stabilization: Participants will be inducted onto buprenorphine prior to beginning the buprenorphine taper. Induction may occur up to 3 weeks prior to admission to the CRU. Participants will be required to show evidence of opioid withdrawal (as per ratings on the COWS) and will receive incremental doses of buprenorphine throughout the day, up to a maximum of 16mg of buprenorphine on the induction day. The induction protocol will be conducted as clinically indicated, based upon medical team recommendations. To increase comfort during the induction, the medical team may administer the PRN concomitant medications that are approved for the taper protocol as well as clonidine. Participants may then be maintained on buprenorphine as an outpatient for up to 3 weeks before CRU admission. Briefly maintaining participants on buprenorphine will enable the study to retain participants between Screening and CRU admission, as the CRU has restricted access for protocols requiring weekend coverage. Participants who are maintained on buprenorphine as an outpatient will receive blister packages of sublingual buprenorphine for outpatient administration and may receive up to 24mg/day (beginning the day after induction) during this period. During the stabilization period between Screening and Admission, participants will be required to visit the clinic on a weekly basis to exchange blister packages. Participants may receive assistance (e.g., bus tokens) from the study to help facilitate transportation to the BPRU on those days. Any participant receiving >16 mg as an outpatient will be transitioned to 16mg on the CRU admission day. Participants who are inducted onto buprenorphine on the CRU admission day will follow an identical induction procedure and will only receive up to 16mg.

Clinical Research Unit (CRU): Following confirmation of eligibility, participants will be admitted onto a residential CRU that is located on the Bayview Medical Campus. Participants will reside on the CRU for up to 11 days (10 nights) and will be allowed to smoke cigarettes ad libitum in a designated smoking area during their stay. Female participants will provide a sample of blood upon admission that will be analyzed for levels of progesterone and estrogen.

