Brief Sleep Hygiene Education: During stabilization, staff will conduct a brief educational session with participants to provide information regarding appropriate sleep hygiene (Doshi et al., 2017). This session will ensure all participants have the same understanding of healthy sleep behaviors before the taper begins, to minimize the impact that differences in sleep hygiene has, and better isolate the impact of SUVO on study outcomes.

Overdose Education: During the stabilization period, participants will also complete a brief opioid overdose prevention computerized education session (developed by Co-I Dunn under NIDA R21DA035327).

Randomization to Group: Participants will be stratified into experimental group based on (a) baseline Pittsburgh Sleep Quality Index (PSQI) (<5/≥5), (b) peak SOWS ratings during buprenorphine induction (≤10/>10), (c) buprenorphine stabilization dose (<16mg/16mg), and (d) sex (M/F). Randomization will occur via a minimization procedure to balance the distribution of these characteristics

across the experimental groups. Study pharmacist staff, who have no direct participant contact, will oversee randomization and dispensing of study medications.

Taper Phase (4 days): Participants will undergo an open-label, step-wise buprenorphine taper. An open-label phase is necessary because buprenorphine placebo tablets/filmstrips are not available; however, this open-label design feature is of value because it increases the overall generalizability of the study results.

Post-taper Phase (4 days): Participants will continue study participation for four days (three nights) following buprenorphine discontinuation, to capture the full course of opioid withdrawal.

Study Medications: Double-blind study medication dosing will begin on the evening before Taper Day 1. Study medications will either be 20mg SUVO, 40MG SUVO, or placebo, which will be administered prior to bedtime. Though participants will be reminded to practice good sleep hygiene, no contingencies or consequences will be associated with their sleep behavior. This is because our extensive experience suggests that participants who are unable to sleep at night will attempt to sleep during the day; all sleep attempts will be captured by wrist actigraphy and nightly questionnaires and evaluated as outcome data. Placing contingencies on sleep parameters (such as no day-time sleeping) could also prompt attrition.

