Upon study completion, participants will be discharged with referral to ongoing OUD treatment and will be provided with take-home dose of intranasal naloxone (Narcan, Adept Pharmaceuticals).

Follow-up: Participants will also complete a follow-up visit approximately 5-10 days after study discharge, during which outcomes including adverse events, suicidality and depressive symptoms, need for additional OUD treatment referral, past 7-day day sleep, and illicit drug use (as assessed via self-report and a urine sample) will be collected.

Study Measures

Objective Sleep Measures:

Sleep Profiler™ Wireless EEG Monitor: The Sleep Profiler™ (Advanced Brain Monitoring, Inc.) is an unobtrusive wireless EEG device that was designed for patients to use in their home sleep environment without the assistance of a professional technician. We will train our research staff and the CRU nursing staff to assist participants with application of the device nightly so we may ensure good measurement fidelity throughout the study. The Sleep Profiler™ runs on a continuous charge for approximately 16 hours and provides three channels of frontal EEG, a pulse rate, and a sensor to detect head movement. The device is lightweight (2.5 oz) and utilizes three proprietary, pre-gelled, self-adhesive, snap electrodes. It can be comfortably applied and strapped to the forehead in 5 minutes and features a built-in impedance check to protect against poor connections, which audibly prompts the user to reaffix the electrodes when impedance is high. Participants will begin wearing the Sleep Profiler™ on Stabilization day 1, which will familiarize participants with the product before they experience withdrawal, and provide baseline data for statistical comparison. Participants will be instructed to affix the Sleep Profiler after receiving their dose of study medication and to remove it upon waking every morning.

Wrist Actigraphy: Participants will wear a triaxial accelerometer (Actigraph wGT3X-BT, Actigraph, LLC) on their non-dominant wrist for the entire duration of study enrollment. Wrist-worn actigraphy has been validated against PSG and provides an acceptable alternative measure of sleep continuity.

Self-report Sleep Measures: Additional self-report measures of sleep will be collected as part of the Primary Study Aims to corroborate quantitative analyses and increase the breadth of sleep data available. These will include measures such as:

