Buprenorphine: Buprenorphine is FDA-approved for the treatment of OUD and it will be used according to that indication in this study. The buprenorphine stabilization and taper will be open label. Participants will be stabilized on buprenorphine for a maximum 3 week period before study admission, and will then complete a 3-day stabilization period (e.g., 8-16mg/day) and a 4-day step-wise taper. These approaches are standard clinical practice. This study utilized the open label taper approach in order to increase ecological validity of the supervised withdrawal paradigm.

Concomitant Medications: Consistent with standard clinical practice treatment, the following concomitant medications will be available to patients upon request: ibuprofen, acetaminophen, loperamide, milk of magnesia, and simethicone. Clonidine may be provided during the induction period only. Concomitant medications introduce a necessary confound in opioid withdrawal research because they reduce the withdrawal symptom severity that is being evaluated as part of the primary study outcomes. However, our considerable experience with opioid withdrawal studies suggests that provision of some additional supportive medications is necessary to prevent treatment attrition. Following randomization to experimental group, patients will not receive additional sleep aids or clonidine. Concomitant medication use will be PRN and compared across groups as an outcome.

- b. Justification and safety information if FDA approved drugs will be administered for non-FDA approved indications or if doses or routes of administration or participant populations are changed.

Suvorexant (SUVO): Suvorexant is approved by the FDA for the indication of insomnia at a 10mg and 20mg dose, so an IND will be requested from the FDA for the doses (20mg, 40mg) proposed in this trial. The proposed 40mg dose is being evaluated because suvorexant has a broad therapeutic window, persons with OUD might have increased orexin signaling, as evidenced by postmortem studies citing 54% more orexinergic neurons in the lateral hypothalamus of persons with OUD compared to healthy controls, and because sleep disturbance during opioid withdrawal is severe and- as of yet- no sleep-promoting pharmacotherapies have been shown to be effective in human opioid withdrawal studies.

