The first primary outcome for this study will be total sleep time during opioid withdrawal as determined by EEG, and supplemented by actigraphy and self-report.

The second primary outcome for this study is abuse liability, which will be assessed via next day measures of Drug Liking measured on a 0-100 point VAS.

b. Secondary outcome variables.

(1) Secondary outcomes from the Sleep Profiler EEG will include measures of sleep continuity and architecture

(2) Secondary actigraphy outcomes will include sleep and activity-related outcomes

(3) Secondary self-report sleep ratings will include self-reported sleep measures

(4) Opioid withdrawal severity, assessed via the subjective opiate withdrawal scale.

(5) Other secondary outcomes include a hypothetical purchasing task, other self-report VAS measures of abuse liability (e.g. drug effect, good effect, bad effect, perceived drug value), self-reported measures of drug craving, VAS opioid withdrawal, stress; diurnal cortisol; vital signs; and retention in treatment.

c. Statistical plan including sample size justification and interim data analysis.

Power Analyses: In order to support the planned 2 and 3 group analyses (comparing 20mg SUVO, 40mg SUVO, and placebo), we used G-power to derive sample sizes from previously reported effect sizes in clinical trials on SUVO and hypothetical opioid purchase task data; both displayed large effect sizes (≥ 0.70). A total sample size of 36 participants (12 per group) would provide 95% power to detect an effect size of 0.70 for difference in total sleep time (Primary Aim 1) and difference in the opioid demand curve (Secondary Aim 1). A study on the abuse liability of SUVO, zolpidem, and placebo in non-ODU patients (Schoedel et al., 2016) reported a medium to large effect size on drug liking (0.45), suggesting a total sample size of 34 would provide 90% power to detect an effect size of 0.45 for Primary Aim 2. To protect against participant drop out, we are proposing to enroll 15 participants per medication group (total N=45).

Analyses: All Primary Outcomes (total sleep time, opioid withdrawal severity, and abuse liability) will be compared as a function of group (20mg SUVO, 40mg SUVO, and placebo; or SUVO [collapsed] vs placebo) and phase (taper vs. post-taper), as well as group by day (7 nights) using 2-factor Proc Mixed analyses with Tukey posthoc testing. Both peak values and Area-under-the-curve (AUC) values of total sleep time, SOWS scores, and Drug Liking

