will be derived for (a) the entire study, (b) the taper period, and (c) the post-taper period. These outcomes will be compared as a function of group and group x phase using independent groups t-tests and ANOVAs with Tukey post-hoc for pairwise comparisons. If data does not meet ANOVA assumptions, mixed model regressions will be used.

Secondary outcomes from the Sleep Profiler EEG may include measures of sleep continuity (sleep latency, sleep efficiency [total sleep time/time spent in bed], wake after onset [WASO], number of awakenings) and architecture (time spent in stage 1, stage 2, stage 3, and rapid eye movement [REM] sleep). (b) Secondary actigraphy outcomes may include wake after sleep onset (WASO), time spent napping, number of naps, and total activity. (c) Secondary self-report ratings may include subjective WASO, VAS sleepiness and quality of sleep, and Stanford Sleepiness Scale score. **Analyses:** All outcomes will be compared as a function of group (20mgSUVO, 40mg SUVO, and placebo) and phase (taper vs. post-taper), as well as group by day (7 nights) using 2-factor Proc Mixed analyses with Tukey posthoc testing. Area-under-the-curve (AUC) values for the entire study and the taper and post-taper periods will then be derived and compared as a function of group and group x phase using independent groups t-tests and ANOVAs with Tukey post-hoc for pairwise comparisons. If data does not meet ANOVA assumptions, mixed model regressions will be used.

Secondary actigraphy outcomes may include wake after sleep onset (WASO), time spent napping, number of naps, and total activity. Secondary self-report ratings may include subjective WASO, visual analogue scale (VAS) sleepiness and quality of sleep, and Stanford Sleepiness Scale score. All outcomes will be compared as a function of group (20mg SUVO, 40mg SUVO, and placebo) and phase (taper vs. post-taper), as well as group by day (7 nights) using area-under-the-curve (AUC). The taper and post-taper periods will then be derived and compared as a function of group and group x phase using independent groups t-tests and ANOVAs with Tukey post-hoc for pairwise comparisons. If data does not meet ANOVA assumptions, mixed model regressions will be used.

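### EEG sleep is recorded before the first study dose to serve as baseline, but no total-sleep-time analysis adjusts for it

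*Combined protocol and SAP*

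**What the plan says.** Section 4a (Objective Sleep Measures) starts the EEG recording on the first stabilization day, to accustom participants to the device and to "provide baseline data for statistical comparison".

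Section 7c (Analyses) compares total sleep time by group and phase, where phase has two levels (taper and post-taper), "as well as group by day (7 nights) using 2-factor Proc Mixed analyses with Tukey posthoc testing". Peak and AUC values "will be derived for (a) the entire study, (b) the taper period, and (c) the post-taper period", and are compared by t-tests and ANOVAs with Tukey contrasts. The fallback to mixed model regression names no covariate. The exploratory regressions do not name baseline EEG. The four minimization factors, including dichotomized PSQI, are used for allocation but are not listed as model terms.

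The timing is spread over several sections:
- Section 6a: participants "will then complete a 3-day stabilization period" and then a 4-day taper.
- Section 4a, Study Medications: "Double-blind study medication dosing will begin on the evening before Taper Day 1".
- Section 4a, Post-taper Phase: "Participants will continue study participation for four days (three nights) following buprenorphine discontinuation".
- Section 4a, Clinical Research Unit: a stay of up to 11 days and 10 nights.

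**The concern.** The protocol gives the early EEG nights a statistical purpose that the analysis section does not carry out. In a trial of 36 to 45 participants in three arms, a pre-treatment measure of the primary outcome is usually the most useful covariate available, and here it is already being collected. Section 1 says the most efficacious dose goes forward to a later study, so the width of the between-arm intervals matters as well as the overall test.

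Leaving the role of baseline open also leaves choices to be made after the data are seen. The plan does not propose either of the following, but it does not rule them out:
- A change score, which is less precise than no adjustment when r is below 0.5.
- Treating all stabilization nights as baseline. On the stated schedule the third is already a dosed night, so this would adjust away part of any drug effect.

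The AUC for the entire study is not defined, so it is unclear whether pre-dose nights enter it as outcome.

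**Working it through.** **Which nights precede study drug.** The phases are 3 stabilization, 4 taper and 4 post-taper days: 3 + 4 + 4 = 11 days, hence 10 nights. The first dose is on the evening before Taper Day 1, which is stabilization night 3. The nights are therefore 2 pre-dose + 1 first dosed + 4 taper + 3 post-taper = 10. This agrees with the 10-night stay and with the 10 nightly EEG bonuses in Section 10. The 7 analysed nights are most likely 4 taper + 3 post-taper, which would leave the first dosed night outside the model; the plan does not list them.

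**The plan's own power figure.** One-way ANOVA with three groups, N=36, 0.70 read as Cohen's f and alpha 0.05 (assumed, not stated): noncentrality 36 × 0.70² = 17.64, power 0.957. The stated 95% reproduces and is not disputed.

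**Effect of one baseline covariate.** Let r be the correlation between baseline and the participant-level outcome. The documents give no r, so a range is assumed. For three arms and one covariate:

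- variance ratio R = (1 − r²) × [1 + 1/(N − 5)]; the bracket is 1 + 1/40 = 1.025 at N=45 and 1 + 1/31 = 1.032 at N=36
- Tukey half-width in outcome SDs = q(0.95; 3, df)/√2 × √(2R/n), with n per arm and R = 1 if unadjusted; df goes from 42 to 41 at N=45 and from 33 to 32 at N=36
- equivalent unadjusted sample size = N/R

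| r | R, N=45 | Equivalent N | Half-width, N=45 | R, N=36 | Half-width, N=36 |
|---|---|---|---|---|---|
| unadjusted | 1 | 45 | 0.887 | 1 | 1.002 |
| 0.3 | 0.933 | 48 | 0.858 | 0.939 | 0.972 |
| 0.5 | 0.769 | 59 | 0.779 | 0.774 | 0.883 |
| 0.7 | 0.523 | 86 | 0.642 | 0.526 | 0.728 |

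At r = 0, R is 1.025 or 1.032. Setting R = 1 gives a break-even r of 0.16 (N=45) or 0.18 (N=36).

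These figures are for a comparison of three arms on one value per participant, such as an AUC or a mean over nights. They do not apply to the group-by-phase interaction or to Tukey contrasts over group-by-day cells.

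**Change score.** With equal variances the ratio is 2(1 − r): 1.4, 1.0 and 0.6 at r = 0.3, 0.5 and 0.7.

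**Missing baselines.** If 3 participants lacking a baseline are excluded, r = 0.3 gives 0.91 × (1 + 1/37) × 45/42 = 1.00 at N=45 and 0.91 × (1 + 1/28) × 36/33 = 1.03 at N=36, so the gain is gone. Simulation with baselines missing at random (20,000 trials per setting) agrees: 0.999 and 1.027. Filling the missing values with the mean over all arms keeps the gain: 0.939 and 0.945. Type I error was 4.7–5.2% for the unadjusted, exclusion and imputation analyses.

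**The case against.** The strongest reply is that this is a matter of efficiency and not an error. The unadjusted test is valid. On the plan's own effect size, power is already 95.7% and rises only to 97.2% at r = 0.3. That stands. The gain matters more if the true effect is smaller: at f = 0.50 and N=36, power goes from 0.729 to 0.770 at r = 0.3 and 0.849 at r = 0.5.

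The second reply is that r may be low. Nights 1 and 2 are the first on the unit and with the device. Some people arrive after up to 3 weeks of buprenorphine, while others are inducted on admission: "Participants who are inducted onto buprenorphine on the CRU admission day will follow an identical induction procedure". Section 6a allows clonidine during induction, which may affect night 1 for the second group. This also stands. At r = 0.2 the N=45 half-width moves only from 0.887 to 0.881 SD, and the r = 0.7 row should not be taken as a forecast. But the possible loss is about 3% of variance at most, and any r above about 0.18 is a net gain.

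Third, a statistical comparison could mean a descriptive baseline table. The wording permits that, but it would leave a pre-treatment measure of the primary outcome unused in estimating the effect. Finally, dose choice will not rest on sleep time alone, since Section 6a speaks of risk and benefit; interval width on the primary outcome is still one input.

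**Conclusion.** The concern holds. The documents collect a pre-dose EEG baseline, state a statistical purpose for it, and name no analysis that adjusts for it. The omission is certain; the benefit depends on an unknown r. Under the assumed values, variance falls by about 7% at r = 0.3 and 23% at r = 0.5, and the Tukey half-width falls from 0.89 to 0.86 or 0.78 SD at 15 per arm. These figures assume complete baselines and a linear relation with a common slope across arms. There is no bias in the planned analysis and no fault in the stated sample size for total sleep time. The change is recommended for precision and to close an analyst choice; the trial's validity does not depend on it.

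**What to change.** Add to Section 7c:

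- **Baseline.** Mean EEG total sleep time over the stabilization nights before the first dose of blinded study medication (nights 1 and 2 on the stated schedule), entered as one continuous covariate in the primary Proc Mixed model and in an ANCOVA for the AUC summaries.
- **Missing baseline.** If one night is missing, use the other. If both are missing, use the mean of all participants regardless of arm. Exclude nobody; a standard mixed model otherwise drops records with a missing covariate.
- **Sensitivity analysis.** Keep the unadjusted model.
- **Nights.** List the 7 analysed nights, say where the first dosed night belongs (not in the baseline), and define the AUC for the entire study.

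Three smaller clarifications would help:
- Say when recording starts on nights 1 and 2, because the wear instruction is tied to a dose not yet being given: "Participants will be instructed to affix the Sleep Profiler after receiving their dose of study medication".
- Apply the same approach to actigraphy, diary sleep time and SOWS where a pre-dose value exists. Study-drug liking has none.
- State whether the four minimization factors enter the primary or a supporting model; either is acceptable. In simulation with assumed factor prevalences of 0.4–0.7, baseline plus the four factors cost about 4–5% (N=45) or 5–8% (N=36) in variance.

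The cost is a few sentences, one degree of freedom for the baseline covariate, and no new data or visits.

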This study is designed as a dose-finding study of SUVO compared to placebo. Briefly, OUD patients seeking supervised withdrawal will be admitted into a clinical research unit and stabilized onto buprenorphine before being randomly assigned to study condition. All participants will then undergo a routine buprenorphine taper, followed by a post-taper phase. Participants will be randomized to receive either placebo, SUVO 20mg, or SUVO 40mg and we hypothesize that one or both doses of SUVO will improve total sleep time relative to placebo. The dose of SUVO identified as most efficacious in this study will be used in a subsequent study. This study is supported by power analyses that were conducted for both Aims 1 and 2. Primary outcomes of this study include total sleep time as measured via an ambulatory electroencephalography (EEG) device, wrist actigraphy, and self-reported sleep as well as abuse liability measures of SUVO. Participants will be referred to ongoing treatment following completion of the study and will be provided with opioid overdose education and Narcan as an additional prevention measure.

2. Objectives (include all primary and secondary objectives)

- **Primary Aim 1: Evaluate whether 20mg and 40mg suvorexant, relative to placebo, improves total sleep time among patients undergoing routine opioid withdrawal, assessed via (a) EEG, (b) actigraphy, and (c) self-report.**

- Primary Aim 2: Evaluate the abuse liability of 20mg SUVO versus 40mg SUVO relative to placebo using self-report ratings, and secondary measures that include a hypothetical purchase task and drug ratings.
 - Secondary Aim 1: Evaluate whether 20mg SUVO and 40mg SUVO decreases self-reported measures of drug effects and craving, opioid withdrawal, concomitant medication use, and self-reported stress; decreased diurnal salivary cortisol and serum cortisol/adrenocorticotropic releasing hormone; and improves treatment retention relative to placebo.
3. **Background** (briefly describe pre-clinical and clinical data, current experience with procedures, drug or device, and any other relevant information to justify the research)

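### Single-step Tukey on the three group means is valid but needlessly conservative: with exactly three arms, a step-down version keeps the same familywise error and has more power to show a second difference

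*Combined protocol and SAP*

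**What the plan says.** Section 7.c (Analyses) compares the primary outcomes across "group (20mg SUVO, 40mg SUVO, and placebo; or SUVO [collapsed] vs placebo", by phase, "as well as group by day (7 nights) using 2-factor Proc Mixed analyses with Tukey posthoc testing". Peak and area-under-the-curve summaries of the same outcomes are then compared "using independent groups t-tests and ANOVAs with Tukey post-hoc for pairwise comparisons". The section gives no alpha, no sidedness and no list of contrasts. It does not say whether Tukey covers the three group means or the group-by-phase and group-by-day cells.

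The questions to be answered are in sections 1 and 2:

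- **Hypothesis:** "we hypothesize that one or both doses of SUVO will improve total sleep time relative to placebo".
- **Primary Aim 1:** "Evaluate whether 20mg and 40mg suvorexant, relative to placebo, improves total sleep time among patients undergoing routine opioid withdrawal". This is two dose-placebo contrasts.
- **Primary Aim 2:** "Evaluate the abuse liability of 20mg SUVO versus 40mg SUVO relative to placebo using self-report ratings". This brings in the comparison between doses.
- **Dose choice:** "The dose of SUVO identified as most efficacious in this study will be used in a subsequent study". Section 6.a also makes the relative risk and benefit of the two doses a reason for having both.

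All three pairwise comparisons of the arms therefore serve a stated purpose.

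**The concern.** Single-step Tukey holds every pair to a limit calibrated for the largest of the three differences under complete equality. With three means that is stricter than it needs to be after one difference has been established. The trial plans 12 to 15 participants per arm and must carry one dose forward, so it needs a first significant difference and also a second one: the other dose against placebo, or 40 mg against 20 mg. The unnecessary strictness falls on that second finding.

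**Working it through.** **Inputs.** Three arms, 12 per arm in the power statement, 15 per arm enrolled, effect size 0.70 and 95% power for Aim 1 (section 7.c). Assumed because not stated: two-sided 5%, normal data, equal variances, equal arm sizes, and one summary value per participant.

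**The plan's own figure.** Read 0.70 as Cohen f in a one-way three-group F test. The noncentrality is f² × N = 0.49 × 36 = 17.64. With 2 and 33 degrees of freedom the power is 95.7%, which reproduces the stated 95%. Read as 0.70 SD between two arms of 12, the power is 37%, which does not. So 0.70 is taken as f below. This 95% is power for the overall test, not for any one pair.

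**Why a second step is allowed.** There are three pairwise null hypotheses. If any two are true, the third is true as well, so the only joint null to protect is that all three means are equal. A gate at the three-group Tukey limit protects that one at 5%. Each single pair then needs only an ordinary 5% test. Any pair beyond the Tukey limit opens the gate and also exceeds the lower t limit, so no Tukey rejection can be lost.

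**Critical |t|.**

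| N (df) | Unadjusted | Tukey, 3 means |
|---|---|---|
| 36 (33) | 2.03 | 2.45 |
| 45 (42) | 2.02 | 2.43 |

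**Effect patterns giving f = 0.70.**

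- Equally spaced means 0, δ, 2δ have SD δ√(2/3). Setting this to 0.70 gives δ = 0.857, so the doses lie 0.857 and 1.715 SD above placebo.
- Equal dose effects 0, δ, δ have SD δ√2/3, giving δ = 1.485.

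**Simulated power, single-step Tukey to step-down Tukey** (at least 200,000 trials per scenario).

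| Per arm; 20 mg, 40 mg effect (SD) | 20 mg v placebo | 40 mg v placebo | Both doses v placebo |
|---|---|---|---|
| 15; 1.0, 1.0 | 62% to 69% | 62% to 69% | 47% to 61% |
| 15; 0.70, 0.70 | 31% to 37% | 31% to 37% | 17% to 28% |
| 12; 0.857, 1.715 (f = 0.70) | 37% to 53% | 95% to 96% | 37% to 53% |
| 12; 1.485, 1.485 (f = 0.70) | 87% to 92% | 87% to 92% | 80% to 89% |

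With 15 per arm and effects of 0.5 and 1.0 SD, power for 40 mg against 20 mg rises from 16% to 24-25%, while 40 mg against placebo moves only from 62% to 64%.

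**Error control.** With all means equal, both methods reject something in 5.0% of trials. With one dose null and the other effective, the null dose is declared different from placebo in at most 5.0% of trials.

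**Which gate.** An overall F test is also a valid gate for three means. However, in up to about 1.6% of trials it stays closed on a difference that Tukey would have declared. The range gate never does.

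**Within night.** There are 2 × 7 = 14 same-night dose-placebo contrasts. With no true effect and an assumed within-person correlation of 0.3 to 0.7, testing them all unadjusted gives a familywise error of about 30-45%. Holm over the 14 gives 3-4%.

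**The case against.** Tukey is pre-specified, valid and conventional for a three-arm dose-finding study, and it supplies simultaneous confidence intervals. That stands, and it is why this is an efficiency point.

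The stated hypothesis is that one or both doses work, and the gate is Tukey's own limit. The chance of rejecting at least one of the three pairs is therefore identical by construction (78% either way with 15 per arm and both doses at 1.0 SD). This also stands: the gain lies in further differences after the first.

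The gain depends on the effect pattern. With 15 per arm and f = 0.70, equal dose effects give 94% against 97% per dose. With equal spacing the weaker dose goes from 47% to 63% and the stronger stays at 99%.

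The change is not free. If Tukey intervals are kept for reporting, some pair will be declared significant while its interval includes zero. This happens in about 12-28% of trials in the four tabulated scenarios. It is the same event as the extra rejection, but a reader will see an inconsistency unless it is explained.

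Two stronger readings are tempting:

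- A reader might infer that Tukey spends error on a comparison nobody asked for. Among the three group means the documents do not support this, because Primary Aim 2 and the choice of dose need 40 mg against 20 mg.
- A reader might infer that Tukey will be run over all interaction cells. That would be 6 × 5 / 2 = 15 pairs by phase, or 21 × 20 / 2 = 210 pairs by night. Of the 210, 14 are same-night dose-placebo contrasts and 7 are same-night 40 mg against 20 mg, which leaves 189 that answer no aim. The limit at N=45 would rise to 2.99 or to about 3.6-3.8. The plan does not say this is intended. What can fairly be said is that the wording leaves open which means Tukey covers.

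**Conclusion.** This is a worthwhile low-cost improvement and not an error in the plan. For one outcome and one set of three group means, step-down Tukey holds familywise error at the same 5%, keeps every Tukey rejection, and adds power for a second difference. The gain is about 7 points per dose and 14 for both doses at 1.0 SD with 15 per arm, and about 16 points for the weaker dose at the plan's own effect with 12 per arm and equal spacing. It is near zero for the stronger dose in that case.

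The figures rest on an assumed two-sided 5%, normal data with equal variances, balanced arms and assumed effect patterns. They do not show that the planned analysis inflates error. Nor do they settle multiplicity across the outcomes treated as primary, the peak and area-under-the-curve summaries, the separate periods, or the alternative of pooling the two doses. Neither method addresses those.

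**What to change.** In section 7.c, for each primary outcome:

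1. State alpha and sidedness, and list the three pairwise group contrasts.
2. State that Tukey applies to the three group means, not to the group-by-phase or group-by-day cells.
3. Compare the largest pairwise difference with the three-group Tukey limit. If it passes, test each of the three pairs at unadjusted two-sided 5%. If not, stop. Use this range gate and not an F gate. In practice, if the smallest Tukey-adjusted p-value is at most 0.05, the three unadjusted p-values are read.
4. Within a phase or night, test only pre-specified same-phase or same-night contrasts, with a Holm adjustment. Do not carry the two-step rule over to the cells, because it is valid only for three means.
5. Keep the Tukey intervals for the three group differences, and state that such an interval may include zero for a pair the step-down test declares significant.

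The cost is analysis-plan wording and a few lines of code. No extra participants or data are needed. Multiplicity across outcomes and summary measures needs its own rule.
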